4.3.4 Supplementary analyses

The following supplementary analysis will be performed:

As-observed analysis (Including all data after taking highly influential prohibited medications and/or highly influential rescue medications)

The data collected after taking the highly influential prohibited medications and/or highly influential rescue medications will be included in the supplementary analysis to evaluate the robustness of the primary analysis results with respect to the intercurrent event handling strategy. Missing ice cube provocation test result at Week 24 will be considered as positive.

4.3.5 Subgroup analyses

To assess the homogeneity of the treatment effect across various subgroups, analyses will be performed on the primary endpoint across the following subgroups:

- Age group (< median, \geq median; adult, adolescent)
- Gender (Male, Female)
- Baseline weight (< median, \geq median, <60 , ≥ 60 kg)
- Baseline BMI (<25 , ≥ 25 - <30 , ≥ 30 kg/m²)
- Region (see [Section 5.3](#))
- Race (White, all the Others)
- Ethnicity (Hispanic, non-Hispanic)
- Baseline H1-AH use (regular vs per-need)
- Baseline serum Total IgE (<100 IU/mL, ≥ 100 IU/mL)
- Duration of cold urticaria before screening visit (<5 , ≥ 5 years)
- History of allergy (Allergic, non-Allergic)
- History of angioedema

To assess the consistency of the treatment effects across the subgroup levels, subgroup analyses will be conducted for the primary endpoint at Week 24. The analysis will be performed based on imputed datasets from the primary analysis.

To test the interaction between intervention and subgroup factor, a logistic regression model incorporating subgroup-by-treatment interaction will be built for each subgroup factor. The model will include all the covariates in the main statistical model plus the subgroup variable (if not one of the covariates adjusted in the main model already) and the subgroup-by-treatment interaction.

In each subgroup, the primary endpoint will be analyzed using the primary approach for the primary endpoint, but on the specific subgroup. Forest plots will be provided.

4.4 SECONDARY ENDPOINT(S) ANALYSIS

4.4.1 Key/Confirmatory secondary endpoint(s)

4.4.1.1 *Definition of endpoint(s)*

Key secondary endpoints are listed below.

- Change from baseline in local wheal intensity at the provocation site at Week 24 using the wheal intensity Likert scale ranging from 0 to 5 (clinician evaluation)
- Change from baseline in the proportion of cold urticaria sign and symptom free days at Week 24 on cold exposure days as measured by ColdUAS

Wheal intensity Likert scale

The Wheal intensity Likert scale (ranging from 0 to 5) is a clinician-reported outcome measure completed at the study visit, 10 minutes after removal of the ice cube from the participant's arm. This scale is comprised of a single item assessing the intensity of patients' cutaneous reaction rated as follows: 0=no wheals; 1=numerous small, non-coalescent wheals; 2=a large, regular, slightly edematous, coalescent wheal; 3=a large and moderately edematous wheal; 4=a large, regular, and significantly edematous wheal without pseudopodia; and 5=a large, very edematous wheal with pseudopodia

Proportion of cold urticaria sign and symptom free days on cold exposure days as measured by ColdUAS

The ColdUAS is a disease-specific PRO questionnaire designed to determine cold urticaria disease activity which is administered daily via e-diary (the details can be found in the protocol). The proportion of cold urticaria sign and symptom free days is defined in two steps: (1) take a window of 14 days before each visit date (i.e., Baseline, Week 12 and Week 24), count the number of days when the patient reports "exposed" to cold (i.e., ColdUAS Q3>0); (2) within the "exposed" days, count the number of days when the patient reports no ColdU related sign and symptom (i.e., ColdUAS Q1=0 and Q2=0). If the number of exposure days is zero, then the

proportion is set to missing, otherwise, it is the ratio of the sign and symptom free days over the exposure days in the 14-day window.

The e-diary completion days should be no less than 6 and exposure days should be no less than 1 in the 14-day window, otherwise the proportion of sign and symptom free days is considered as missing. Additionally, analyses based on exposure days no less than 3 will be conducted.

4.4.1.2 Main analytical approach

The intercurrent event handling strategy for the key secondary endpoints is the treatment policy/composite approach.

This key secondary endpoints will be analyzed using an analysis of covariance (ANCOVA) model with baseline value of the endpoint, treatment group, region (combined countries), and background H1-antihistamine regular/daily use (Yes/No) as covariates, with intercurrent events and missing data being handled by a hybrid method of the worst-observation carried forward (WOCF) and multiple imputation. For participants who took highly influential prohibited medications and/or highly influential rescue medications (see [Table 4](#)), their data after the medication usage will be set to missing, and worst post-baseline value on or before the time of the medication usage will be used to impute missing Week 24 value (for participants whose post-baseline values are all missing, the baseline will be used to impute). Participants who discontinue the treatment prematurely are encouraged to follow the planned clinical visits. For participants who did not take the highly influential prohibited medications and/or highly influential rescue medications, all data collected after treatment discontinuation will be used in the analysis. For participants who discontinue study intervention due to lack of efficacy, all data collected after discontinuation will be used in the analysis, and a WOCF approach will be used to impute missing Week 24 value if needed (i.e., due to study discontinuation). For participants who discontinue study intervention not due to lack of efficacy, all data collected after discontinuation will be used in the analysis, and a multiple imputation approach will be used to impute missing Week 24 value if needed (i.e., due to study discontinuation). This multiple imputation will use all participants excluding participants who have taken the highly influential prohibited medications and/or highly influential rescue medications on or before Week 24 and excluding participants who discontinue due to lack of efficacy on or before Week 24. Each of the imputed complete data will be analyzed by fitting an analysis of covariance model as described above. Statistical inference obtained from all imputed data will be combined using Rubin's rule. Descriptive statistics including number of participants, mean, standard error, and least squares (LS) mean changes (and standard error) score will be provided. In addition, difference of the dupilumab group against placebo in LS means and the corresponding 95% confidence intervals (CI) will be provided along with the p-values.

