Section 3 Objectives and endpoints/ Section 9.4.1 efficacy analyses	The following tertiary/exploratory endpoints were removed: 
• Change from baseline in [REDACTED] at Week 12 and at Week 24 compared with placebo• Change from baseline in [REDACTED] over time up to Week 24 compared to placebo• Change from baseline in HRQoL as measured by Cold Urticaria Quality of Life (ColdU-QoL) questionnaire at Week 24 compared placebo	[REDACTED] scoring is not validated by the scale developer and therefore the endpoints evaluating change in [REDACTED] score were removed. This endpoint was removed from tertiary endpoints as it was already mentioned as a secondary endpoint (was duplicated by error).

Section # and Name	Description of Change	Brief Rationale
Section 1.1 Synopsis Analysis of secondary endpoints/ Section 9.4.1 Efficacy analyses/ Section 10.13 Appendix 13 - Estimands for main endpoints	
Change in the imputation rule from “worst possible value” to “worst observation carried forward (WOCF) approach” for participants taking highly influential prohibited medications and/or highly influential rescue medications.The following changes related to missing data handling were made: For participants who discontinue study intervention due to lack of efficacy, all data collected after discontinuation will be used in the analysis, and a WOCF approach will be used to impute missing Week 24 value if needed. For participants who discontinue study intervention not due to lack of efficacy, a multiple imputation approach will be used to impute missing Week 24 value, and this multiple imputation will use all participants excluding participants who have taken the highly influential prohibited medications and/or highly influential rescue medications on or before Week 24 and excluding patients who discontinue due to lack of efficacy on or before Week 24.	Handling of missing data after taking highly influential prohibited medications and/or highly influential rescue medications or after withdrawal of study intervention are modified to include each participant's own worst data in order to better reflect the clinical scenario of treatment failure.

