1.3 SCHEDULE OF ACTIVITIES (SOA)

Procedures	Screening (2 to 4 weeks before Day 1)	Intervention period (Weeks)			Follow-up (12 weeks)
		0 (Day 1)	12 ±3 days	24 ±3 days	
Visit	1	2 ^a	3	4 (EOT)	5 (EOS)
Screening/baseline:					
Informed consent	X				
Medical history including systemic hypersensitivity reactions and ACUSI ^b	X				
Prior and concomitant medication ^c	X	X	X	X	X
Demographics	X				
Inclusion/exclusion criteria	X	X			
Patient e-diary training	X				
Randomization		X			
Study intervention					
Call IVRS/IWRS	X	X	X	X	X
IMP administration		←-----X ^d -----→			
Dispense/Upload electronic diary ^e	X	←-----X-----→			X
Dispense EpiPen ^f		X			
Safety^g					
Physical examination ^h	X	X		X	X
Vital signs ⁱ	X	X	X	X	X
Electrocardiogram (12 lead) ^j	X				

Procedures	Screening (2 to 4 weeks before Day 1)	Intervention period (Weeks)			Follow-up (12 weeks) 36 ±7 days
		0 (Day 1)	12 ±3 days	24 ±3 days	
Visit	1	2 ^a	3	4 (EOT)	5 (EOS)
Hematology, biochemistry, urine analysis ^k	X	X	X	X	X
Hepatitis, HIV Serology, TB test ^l	X				
Pregnancy test ^m	Serum	Ur	Ur	Ur	Ur
AE reporting, including SAEs	X	X	X	X	X
Pharmacokinetics and ADA^g					
Serum PK samples for dupilumab concentration ⁿ		X	X	X	X
Anti-dupilumab antibody ⁿ		X	X	X	X
Biomarkers^g					
Serum total IgE		X	X	X	X
Basophil activation test at selected sites (optional) ^o		X	X	X	
Archive serum and plasma samples (optional) ^p		X	X	X	X
DNA (whole blood) samples - Optional ^q		X			
RNA (whole blood) samples - Optional ^r		X		X	

Procedures	Screening (2 to 4 weeks before Day 1)	Intervention period (Weeks)			Follow-up (12 weeks)
		0 (Day 1)	12 ±3 days	24 ±3 days	
Visit	1	2 ^a	3	4 (EOT)	5 (EOS)
Efficacy^g					
Ice cube provocation test ^s	X	X	X	X	X
Wheal intensity Likert scale after provocation test ^t		X	X	X	X
Peak pruritus NRS, peak pain NRS, and peak burning sensation NRS after provocation test		X	X	X	X
ColdUAS	X	X	X	X	
UCT	X	X	X	X	X
DLQI/CDLQI ^u		X		X	
ColdU-QoL		X		X	
PGIC			X	X	
PGIS	X	X	X	X	
EQ-5D-5L		X		X	
Healthcare resource utilization/productivity (missed school/workdays) ^v		X		X	

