3.1 APPROPRIATENESS OF MEASUREMENTS

Primary acquired cold urticaria (ACU) is a type of physical chronic inducible urticaria that is characterized mainly by the appearance of wheals after contact with cold or cooling and rewarming of the skin (4). The assessments used in this study focus on evaluation of local symptoms that occur after skin contact to cold using ice cube provocation test. In addition, overall urticaria control, daily documentation of skin reactions to cold, participant's QoL, reduction in need of rescue therapy and health status are evaluated.

The proposed primary endpoint is proportion of participants with negative ice cube provocation test (absence of a confluent hive/wheal at the entire skin site of exposure) at Week 24. Cold provocation tests are standard in diagnosis of cold urticaria (4). In addition, they are used for assessment of efficacy in clinical trials (23, 24) in patients with ColdU. Cold urticaria symptoms appear only after skin contact with a cold trigger (cold air, liquids, or solid objects), usually within minutes, and persist for up to a few hours. The use of cold provocation tests allows for the standardization of the cold trigger and for performing assessment in predefined time points. The ice cube provocation test will be standardized for the purpose of this study and an operational manual with instructions for ice cube preparation and cold provocation test administration will be provided to the study centers along with the study protocol. This will ensure that all study centers will apply the ice cube provocation tests consistently across this international, multi-center clinical study.

Presence of a confluent hive/wheal as well as wheal intensity will be assessed by the clinicians 10 minutes after removal of the ice cube, as recommended in the CIndU (EAACI/GA²LEN/EDF/UNEV) guidelines (1). Assessment will be performed at each provocation test, ie, at Week 0, Week 12, and Week 24. In addition, symptoms of itch severity, skin burning sensation, and skin pain will be assessed by the participant 10 minutes after the cold provocation test.

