6.5.1 Rescue medicine

All participants will be allowed to take study-defined H1-antihistamine (see [Section 6.1.2](#)) as rescue therapy as long as they do not exceed 4-fold the approved dose for CSU during the screening, treatment, and follow-up periods. If symptoms are still uncontrolled after increase of H1-antihistamine to the maximum allowed dose, or if the participant is already on the 4-fold approved H1-antihistamine, participants can switch to another antihistamine up to 4-fold the approved dose for CSU or a short course of OCS is allowed during the treatment and follow-up periods. In order to ensure consistency, when possible, it is recommended to use OCS for 5 to 7 days with a starting dose of oral prednisone 40 mg (or clinically comparable OCS) followed by taper per the Investigator's judgment.

Due to an episodic nature of ColdU, it is recommended to prescribe rescue therapy for a short period of time (not more than 7 days).

The ice cube provocation test should be delayed if rescue therapy (H1-antihistamine or OCS) is taken within 5 days prior to the test. The ice cube provocation test can be done when the participant is back to prescreening H1-antihistamine dose or is off H1-antihistamine (or OCS) intake for at least 5 consecutive days to allow to have ice cube provocation test performed under the same background condition for each participant from screening visit (Visit 1) to EOS (Visit 5).

In case of systemic hypersensitivity reactions due to cold, the participants may require epinephrine treatment. EpiPen (or a local equivalent) will be provided to the participants at the beginning of the study, and the participants should be appropriately trained how and when to use it. EpiPen use should be in accordance with the locally approved product labeling.

For rescue medication in participants in Japan, please see Appendix 8 ([Section 10.8](#)).

The initial background therapy should remain unchanged throughout the study. Participants should continue their prescreening dose of initial H1-antihistamine once rescue treatment is no longer required or stop H1-antihistamine intake. The use of permitted rescue medications should be delayed in all participants, if possible, for at least 8 weeks following the initiation of the investigational treatment. The date and time of rescue medication administration as well as the name and dosage regimen of the rescue medication must be recorded.

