10.13 APPENDIX 13: ESTIMANDS FOR MAIN ENDPOINTS

Table 11 - Summary of primary estimand for main endpoints in ColdU study

Endpoint Category (estimand)	Estimands				Population-level summary
	Endpoint	Population	Intercurrent event(s) strategy and missing data handling		
Primary objective: To demonstrate the efficacy of dupilumab in adult and adolescent participants with primary acquired chronic inducible ColdU who remain symptomatic despite the use of an H1-antihistamine					
Primary endpoint (treatment policy/composite estimand)	Proportion of participants with negative ice cube provocation test at Week 24	ITT	Discontinuation of the study intervention before Week 24 (but not taking highly influential prohibited medications and/or highly influential rescue medications prior to Week 24): Off-study intervention data up to Week 24 will be included in the analysis (treatment policy strategy). Taking highly influential prohibited medications and/or highly influential rescue medications prior to Week 24: Participants will be considered as having positive ice cube provocation tests at Week 24 (composite strategy). Having missing data at Week 24: Participants will be considered as having positive ice cube provocation tests at Week 24.	CMH test stratified by region (combined countries) and background H1-antihistamine regular/daily use (Yes/No). The comparison of the proportions of treatment response between dupilumab and placebo will be derived, and the corresponding odd ratios and the 95% CI will be reported.	
Secondary objective: To demonstrate the efficacy of dupilumab on primary acquired chronic inducible ColdU local signs and symptoms					

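### For wheal Likert, site NRS and UCT change, the worst post-baseline value of a participant who fails after Week 12 is normally the single pre-failure Week 12 reading, so a confirmed failure can carry response credit to Week 24

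*SAP*

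**What the plan says.** **Imputation rule.** SAP 4.4.1.2 covers the key secondary endpoints. After a highly influential medication, later data become missing and the "worst post-baseline value on or before the time of the medication usage will be used to impute missing Week 24 value". Baseline enters only as a fallback: "for participants whose post-baseline values are all missing, the baseline will be used to impute". SAP Table 2 and Protocol 9.4.1 and Appendix 13 carry the same rule. SAP 4.4.2 applies the same procedure to the site NRS scores and to UCT change.

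**Who it covers.** SAP 4.3.2 and Table 4 limit it to listed medications whose use a blinded medical review attributes to treatment failure. Non-topical corticosteroids are on the list, and their rescue row is marked as not stopping IMP.

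**When the scales are read.** The Schedule of Activities rows "Wheal intensity Likert scale after provocation test" and "Peak pruritus NRS, peak pain NRS, and peak burning sensation NRS after provocation test" are marked at Day 1, Week 12, Week 24 and Week 36. The UCT row has the same visits plus screening. Protocol 3.1 says of the wheal reading: "Assessment will be performed at each provocation test, ie, at Week 0, Week 12, and Week 24". SAP Table 10 has one post-baseline window before the Week 24 window for these scales.

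**Primary endpoint.** The same participant is scored as having a positive ice cube test at Week 24 (SAP Table 2; Protocol Appendix 13).

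**Stated aim.** The protocol's amendment summary says the rule uses each participant's own worst data "in order to better reflect the clinical scenario of treatment failure".

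**The concern.** A worst-observation rule penalises failure only if at least one reading in the set reflects the failed state. Here the set normally holds one reading, taken before the failure, and the untreated state at baseline is left out. A good Week 12 score is then carried to Week 24 for someone the plan itself classes as a treatment failure.

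The rule can also replace real data. Protocol 6.5.1 delays the provocation test until the participant has been off OCS for 5 days, so a Week 24 wheal reading may well exist after rescue. That reading is set to missing even if it is bad.

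Wheal intensity and itch are ranks 2 and 4 in the SAP 4.6 hierarchy, each tested at two-sided 0.01. Credit for failed participants can therefore enter confirmatory tests. The tipping-point and as-observed analyses in SAP 4.3.3 and 4.3.4 are for the primary endpoint. SAP 4.4.1.2 specifies none for these endpoints, so the effect would not be visible in the planned output.

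**Working it through.** **Plan's own figure.** The documents give no planning figure for Likert, NRS or UCT. The only figure used here is 39 per arm, as a denominator. It cannot be reproduced because the response rates are redacted. As a consistency check, take the unpooled Z formula n = [p1(1−p1) + p2(1−p2)](z₀.₉₉₅ + z₀.₉₀)²/(p1−p2)² with assumed rates of 5% and 40%. This gives n = 35, and 35/0.9 = 38.9, or 39 per arm. The point does not depend on this.

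**Step 1: apply the rule to the schedule.** Let B be the baseline score, W the Week 12 score, and assume no extra reading. Every row is a confirmed failure and has a positive ice cube test on the primary endpoint.

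| Case (Likert) | B | W | Medication | Imputed Week 24 | Change |
|---|---|---|---|---|---|
| Full response, then failure | 4 | 0 | Week 16 | 0 | −4 |
| Partial response, then failure | 4 | 2 | Week 16 | 2 | −2 |
| Failure before any post-baseline reading | 4 | none | Week 8 | 4 (baseline) | 0 |

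With baseline in the worst set, all three rows give change 0.

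**Step 2: effect on one arm's mean.** Relative to the baseline-inclusive rule, one affected participant shifts the arm's raw mean change by (B − W)/39 when W is better than B, and by 0 otherwise. Inclusion criterion I 03 requires a confluent wheal at Visit 2, and Likert grade 2 is the first coalescent grade. Baseline Likert is therefore expected to be 2 to 5. With W = 0:

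- Likert: 2/39 = 0.051; 3/39 = 0.077; 4/39 = 0.103; 5/39 = 0.128 (the maximum).
- Itch NRS, baselines assumed: 4/39 = 0.103; 6/39 = 0.154; 8/39 = 0.205; 10/39 = 0.256 (the scale maximum).

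**Step 3: effect on the treatment difference.** The shift is [sum of (B − W) in affected dupilumab participants − the same sum in placebo]/39. Equal sums give 0. A Likert shift of 4 × 4/39 = 0.41 needs four affected participants in one arm, none in the other, each with B = 4 and W = 0.

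**Step 4: scale against noise.** With an assumed SD of 1.0 to 1.5, the standard error of the difference is SD × √(2/39) = 0.23 to 0.34. One unbalanced case with B = 3 and W = 0 (0.077) is then 0.34 to 0.23 standard errors. Four (0.308) are 1.36 to 0.91. The counts and SDs are assumptions, and covariate adjustment would change these figures somewhat.

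**Step 5: could another reading rescue the rule?** The early-discontinuation visit in Protocol 7.1.1 applies only to those who stop IMP, and corticosteroid rescue does not require that. SAP 5.4 lets unscheduled efficacy readings into by-visit summaries, but does not say whether the worst-value search uses them. Either kind of reading helps only if taken on or before the medication.

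**Step 6: where the point stops.**

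- ColdUAS has daily diary data and two-weekly scores from Week 2 (SAP Table 8).
- DLQI and ColdU-QoL have no planned reading between Day 1 and Week 24, so they normally fall back to baseline.
- For the Week 12 versions of the Likert and NRS endpoints, no planned reading precedes Week 12, so baseline is again used.

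**The case against.** **The rule is deliberate and consistent.** Amendment 01 moved from a worst-possible value to the participant's own worst value, and the synopsis, Protocol 9.4.1, Appendix 13 and the SAP agree. A reader might infer a drafting slip or a contradiction between documents; there is none. Binary and continuous endpoints are openly handled differently. This stands, but it does not answer the point. With one pre-failure reading, the participant's own worst data cannot show the failure the amendment wants reflected.

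**Frequency is unknown.** A reader might infer that late failure is likely, because rescue is to be delayed where possible "for at least 8 weeks following the initiation of the investigational treatment". The documents do not support that. The delay covers all rescue, including extra H1-antihistamine, which SAP Table 4 does not count as highly influential. OCS comes later in the rescue sequence, and use must be confirmed as treatment failure. Full credit also needs a floor score at Week 12. No rate is given for this chain.

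**Direction is unknown.** A reader might infer that the rule favours dupilumab. It applies to both blinded arms, and a rescued placebo participant with a good Week 12 score gets the same credit, which could dilute the effect. This stands.

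**Scope is limited.** The point should not extend to participants who discontinue for lack of efficacy. They are due an early-discontinuation visit with all end-of-treatment assessments, and their later data are used. Nor does it reach ColdUAS. Both limits stand.

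**Conclusion.** The point holds for Week 24 change in wheal Likert, site NRS and UCT, after a highly influential medication taken later than Week 12 and confirmed as treatment failure. In those participants the rule normally returns the pre-failure Week 12 value and can credit partial or full response to someone counted as a failure on the primary endpoint. UCT is affected in the same way but is outside the hierarchy.

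The size is at most 0.13 Likert points or 0.26 itch points in one arm's mean per affected participant, assuming 39 per arm and no extra reading before the medication. The figure of 0.41 on Likert should not be read as an expected shift in the treatment difference, because it needs the one-sided pattern in Step 3. The documents support neither a frequency nor a net direction. What they do support is that the rule gives a wrong score in a definable case, at two ranks of the hierarchy, with no specified sensitivity analysis to show it. It should be changed before database lock.

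**What to change.** In SAP 4.4.1.2 and Table 2, add a rule limited to the Week 24 change endpoints for wheal Likert, site itch, burning and pain NRS, and UCT. After a confirmed highly influential medication, impute Week 24 with the worse of the baseline value and every post-baseline value obtained on or before the medication. Worse means higher on Likert and NRS, and lower on UCT. State whether unscheduled readings count. Leave the ColdUAS rule and the lack-of-efficacy rule as they are.

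Keep the current rule as a sensitivity analysis. Record the departure from the protocol in SAP 5.2, which now lists none beyond Amendment 01, and bring the matching sentence in SAP 1.1 into line.

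At minimum, leave the main rule alone and prespecify the baseline-inclusive version as a sensitivity analysis for these endpoints before database lock.

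The cost is a short SAP edit, a documented departure from Amendment 01, and a slightly different, possibly less favourable, estimate. No data collection or clinical conduct changes.
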